4.4.3.5. Hospitalizations and Quality of Life

The final analysis will be based on subjects in the TP. If an interim analysis is performed for the hospitalization endpoint before the final analysis, the analysis will be based on the evaluable subjects defined in [Section 3.12](#); the quality of life endpoints will be presented based on all data available as of the data cut-off.

- **Change from baseline in annualized hospital admissions and days**

The number of VOE-related hospital admissions and in-patient VOE-related hospitalization days from post-drug product infusion discharge through last follow-up will be annualized and compared to the corresponding annualized values during the 2 years prior to Informed Consent. All hospitalizations for 3 groups will also be included data listings. The imputation rules for partial date of admission and discharge can be found in [Appendix 6.1, Table 11](#).

- **Change from baseline in patient-reported quality of life, as measured by PROMIS**

PROMIS-57 is used for subjects ≥18 years old and has 7 domains + 1 pain intensity question. PROMIS-49 (PROMIS Pediatric Profile 49 or PROMIS Parent Proxy Profile 49) is used for subjects <18 years old (from Group C only) and has 6 domains + 1 pain intensity question. Each domain has 8 questions. Standardized score ("T score") will be derived per the raw values from the answers to the questions and corresponding T score reference table.

The descriptive statistics for PROMIS-57 or PROMIS-49 T scores in each domain and pain intensity over time will be presented separately. Baseline is defined the first assessment on or after Informed Consent but before initiation of stem cell collection. Change from baseline will be based on T scores in each domain and raw value in pain intensity question. The number and percentage of subjects with change from baseline of T scores ≥ 5 or ≤ -5 (Terwee et al. 2021), depending on the direction of each domain, will be summarized over time. Likewise, the number and percentage of subjects with change from baseline ≤ -2 will be presented for raw values in pain intensity questions. If different version of PROMIS is used at baseline and post-drug product infusion, change from baseline in some domains will not be calculated if it is considered as incomparable per PROMIS user manual. For example, if the baseline is based on the 8 questions of "Satisfaction with Participation in Social Roles 8a", and the post-drug product infusion is based on the 8 questions of "Ability to participate in social roles and activities 8a", then no change from baseline will be calculated although both domains are for social roles.

The results from each individual question and T scores from each domain will be also presented in the listing.

4.4.4. Analysis of Exploratory Efficacy Endpoints

All exploratory endpoints indicated below will be based on subjects in the TP and summary tables will be presented by group.

- **Change from baseline in cerebral vasculature and prior brain parenchymal injury evaluation at Month 12 and Month 24**

Cerebral MRA/MRI data at Baseline, Month 12, and Month 24 will be presented in a shift table using the following categories: Normal, Abnormal- not clinically significant (NCS), and Abnormal- clinically significant (CS).

TCD (cm/s) data at Baseline, Month 12, and Month 24 may be presented in a listing or a shift table using the following categories: <170 , ≥ 170 and <200 , and ≥ 200 .

- **Change from baseline in bone mineral density (BMD) using DXA at Month 24**

Descriptive statistics for BMD Z scores (g/cm^2) and the corresponding change from baseline will be presented by visit for different locations (such as lumbar spine (L1-L4), right and left proximal femur, whole body less head, and other) for subjects in Group C.

Overall interpretation of BMD at Month 24 will be presented using the following categories: No significant change from baseline, Significant change from Baseline, and Clinically significant Findings.

- **Change from baseline in brain natriuretic peptide (BNP)**

Descriptive statistics will be provided for BNP observed values and change from baseline. Listing will be provided for BNP assessments over time.

- **Change from baseline in patient-reported outcome (PRO) measures**

Descriptive statistics will be provided for the following PRO measures for subjects in Group C. If data are spare, only listings will be provided.

- Overall health, as measured by EuroQol-5D (EQ-5D-3L or EQ-5D-Y)

Descriptive statistics for each parameter over time will be presented for EQ-5D-3L and EQ-5D-Y, separately. EQ-5D index score will be derived only for EQ-5D-3L. Change from baseline will be summarized over time for Health State Today and EQ-5D index.

- Work productivity, as measured by the Work productivity and Activity Impairment Questionnaire-General Health (WPAI-GH or Caregiver WPAI-GH)
Descriptive statistics and change from baseline over time will be provided for each parameter.
- Cognitive function, as measured by PROMIS Short Form 6a (PROMIS-6a)
Descriptive statistics for T scores and change from baseline will be presented over time. The number and percentage of subjects with change from baseline of T scores ≥ 5 (Terwee et al. 2021) will be summarized for each timepoint.

- **Evaluation of chronic pain using AAPT**

Chronic pain will be assessed per the SOE and includes evaluation of the AAPT Diagnostic Criteria for Pain Associated with SCD. Descriptive statistics will be provided. If data are sparse, only listings will be presented.

- **Change from baseline in pain medication use**

Pain medication is defined as opioids if WHO Drug Anatomical Therapeutic Chemical (ATC) level 3 equals to “Opioid”. Number and percentage of subjects who have opioids medication use at baseline and post- drug product infusion by time interval (Day 1 to Day 30, Day 31 to Day 60, Day 61 to Day 90, >3 -6 months, >6 -12 months, >12 -18 month and >18 months post-drug product infusion) will be provided for subjects in Group C. Baseline is defined as within 30 days prior to Informed Consent. Opioid medications will be further categorized as non-oral opioids and oral opioids. All opioid pain medications will be presented in listings.

- **Exploratory assays to assess change from baseline in sickle cell characteristics and bone marrow pathophysiology**

The exploratory assays, such as single cell Western Blot for β -globins (determining $\% \beta^{A-T87Q+}$ RBCs), single colony assays (determining $\% LVV+$ colonies), single cell LVV (determining PB $\% LVV+$ Cells), or ex-Vivo Sickling (determining AUC of sickled RBCs) may be presented, and by-subject results over time may be presented. Depending on results, these results may also be included in correlation analyses. Kinetics including by-subject spaghetti plots may be presented as pharmacodynamics, whereas proportion of subjects with these parameters may be summarized as efficacy.

Bone marrow morphology read locally by investigator will be presented in a by-subject listing. Bone marrow smear morphology analyzed centrally will be summarized by alpha-globin genotype and for Group C subjects in TP, for each time period ($<Day 1$, $\geq Day 1$). The parameters include the number of subjects with dyserythropoiesis noted, abnormal erythroid precursors (%), the number of subjects with dysgranulopoiesis noted, abnormal myeloid precursors (%), the number of subjects with dysmegakaryopoiesis noted, abnormal megakaryocyte precursors (%), erythroid (%) and category ($<30\%$, $\geq 30\%$), Myeloid:Erythroid ratio (%) and category ($\leq 1.1:1$, $>1.1:1$). Details will be provided in listings.

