2.2.1.4. Exploratory Efficacy Endpoints

- Change from baseline in cerebral vasculature and prior brain parenchymal injury evaluation at Month 12 and Month 24 (as measured by cerebral magnetic resonance angiography [MRA]/magnetic resonance imaging [MRI] in all subjects, and transcranial Doppler [TCD] for subjects \leq 16 years old at Informed Consent)
- Change from baseline in bone mineral density (BMD) evaluation using dual x-ray absorptiometry (DXA) at Month 24
- Change from baseline in brain natriuretic peptide
- Change from baseline in Patient reported Outcome (PRO) measures including:
 - Overall health: EuroQol-5D (EQ-5D-3L or EQ-5D-Y)
 - Work productivity, as measured by the Work Productivity and Activity Impairment Questionnaire-General Health (WPAI-GH or Caregiver WPAI-GH)
 - Cognitive function as measured by PROMIS Short Form 6a
- Evaluation of chronic pain using AAPT
- Change from baseline in pain medication use
- Exploratory assays to assess change from baseline in sickle cell characteristics and bone marrow pathophysiology

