5.8. Prior and Concomitant Medication

5.8.1. Prior Medication

All medications taken within 30 days prior to the Screening Visit are to be recorded in the Prior and Concomitant Medication case report form (CRF). Note additional requirements for collection of HU and pRBC transfusion history as detailed in [Section 6.2.1](#) and [Section 6.2.2](#).

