For continuous variables, descriptive statistics such as the number of observations or subjects, mean, standard deviation (SD), median, 25% percentile (Q1) and 75% percentile (Q3) as needed, minimum and maximum values will be presented. Mean, median, Q1, Q3, and 95% confidence intervals (CI) will be rounded to 1 additional decimal place compared to the original data (maximum of 3 decimal places). The SD will be rounded to 2 additional decimal places compared to the original data. Minimum and maximum will be displayed with the same accuracy as the original data. The maximal decimals for SD will be 4.

For categorical variables, summary of the number and percentage within each category of the parameter will be presented. A shift table, for change from baseline, can be provided as appropriate. In the shift table, baseline, the worst value within each visit window post-drug product infusion (if there is more than 1 value), and the worst value during the entire follow-up post-drug product infusion will be presented as needed.

Descriptive summary statistics, as well as 2-sided 95% CI, will be presented on selected parameters, as described in the sections below. The exact CI for proportion will be calculated using Clopper-Pearson exact method.

Longitudinal data (collected serially over time on study) will be presented by appropriate time intervals, such as monthly, quarterly, and so forth, depending on the nature of the data.

For purposes of calculations, a month will be defined as 365.25/12 (30.4375) days and a year as 365.25 days. For reporting by month, calculations will be rounded to the nearest day (i.e., the calculated value at 18 months, 547.9, would be rounded to 548 days; the calculated value at 6 months, 182.6, would be rounded to 183 days).

By-subject listings of data for all completed and discontinued subjects, including screen failures (as appropriate), will be provided. All data listings that contain an evaluation date will contain a relative study day (Rel Day). Pre- and post- drug product infusion study days are numbered relative to the day of drug product infusion, which is designated as Day 1.

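### Any-opioid-use percentages in a 30-day baseline are not comparable with those in the 3- and 6-month windows used after Month 3, so moderate falls in intermittent use appear as increases

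*SAP*

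**What the plan says.** Protocol 2.2.1.4 lists "Change from baseline in pain medication use" among the exploratory efficacy endpoints. SAP 4.4.4 defines pain medication as opioids by WHO Drug class and specifies the summary for Group C as "Number and percentage of subjects who have opioids medication use at baseline and post- drug product infusion by time interval". The intervals are "Day 1 to Day 30, Day 31 to Day 60, Day 61 to Day 90", then >3-6 months, then ">6 -12 months, >12 -18 month and >18 months post-drug product infusion". On the baseline it states: "Baseline is defined as within 30 days prior to Informed Consent". Use is split into oral and non-oral opioids, and all opioid records are listed. No rate, number of days of use, dose or fixed look-back is specified.

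The short baseline matches what is collected. Protocol 5.8.1 says: "All medications taken within 30 days prior to the Screening Visit are to be recorded". By contrast, SAP 3.4 puts VOEs, severe VOEs, hospitalizations and pRBC transfusions on an annualized scale, which removes the dependence on window length for those measures.

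**The concern.** For a subject who uses opioids intermittently, the chance of at least one use grows with the length of the window. A 30-day baseline set beside a 6-month interval therefore mixes two things: a change in use, and more time in which to be counted. Subjects whose use has genuinely fallen can move from not counted to counted.

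Every interval after Month 3 is affected, including those spanning Months 6 to 18, the period of the primary endpoint. The intervals of matching length all lie in the first 90 days, when conditioning, the transplant admission and recovery also influence opioid use. What is at stake is how one descriptive table is read: a reader could not separate a modest or absent reduction in opioid use from the effect of the longer window.

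**Working it through.** The plan gives no expected rate, power or target for this endpoint, so there is no figure of its own to reproduce. The check is how the planned percentage behaves when the true change is known.

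**Window lengths.** SAP 3.2 states that "a month will be defined as 365.25/12 (30.4375) days and a year as 365.25 days".
- Baseline: 30 days.
- >3-6 months: 3 × 30.4375 = 91.3 days; 91.3/30 = 3.04 times baseline.
- >6-12 and >12-18 months: 6 × 30.4375 = 182.6 days; 182.6/30 = 6.09 times baseline.
- >18 months: ends with follow-up at the Month 24 Visit, so about 6 months.

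**Model (assumption).** Opioid episodes occur at a constant rate *r* per year, as a Poisson process. Then P(any use in *w* days) = 1 − exp(−*r* × *w*/365.25). The documents give no opioid episode rate. As an anchor, Inclusion Criterion 3.1 requires at least 4 severe VOEs in 24 months, or 2 per year. One opioid episode per severe VOE is assumed, and higher rates are shown as a range.

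**At 2 per year:**
- Baseline: 1 − exp(−2 × 30/365.25) = 15.1%.
- 6-month interval, no change: 1 − exp(−2 × 0.5) = 63.2%.
- 6-month interval, 50% reduction: 1 − exp(−1 × 0.5) = 39.3%.
- 6-month interval, 75% reduction: 1 − exp(−0.5 × 0.5) = 22.1%.

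**Other assumed rates, 6-month intervals:**

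| Rate before treatment | Baseline (30 days) | No change | 75% reduction | 90% reduction |
|---|---|---|---|---|
| 2 per year | 15.1% | 63.2% | 22.1% | 9.5% |
| 4 per year | 28.0% | 86.5% | 39.3% | 18.1% |
| 12 per year | 62.7% | 99.8% | 77.7% | 45.1% |

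**Break-even.** The two percentages are equal when *r* × 30 = *r*(1 − reduction) × *w*, so reduction = 1 − 30/*w*. The starting rate cancels.
- 6-month intervals: 1 − 30/182.6 = 83.6%.
- >3-6 months: 1 − 30/91.3 = 67.1%.

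**Varying rates between subjects.** With gamma-distributed rates (mean 4 per year, shape *k* = 1), P = 1 − (1 + μ/*k*)^(−*k*), where μ is the mean number of episodes in the window.
- Baseline: μ = 4 × 30/365.25 = 0.329, giving 24.7%.
- After a 75% reduction, 6 months: μ = 1 × 0.5 = 0.5, giving 33.3%.
- The break-even is again 83.6%.

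**Equal 30-day windows, 2 per year.** Baseline is 15.1%. The later figure is 15.1% with no change, 7.9% with a 50% reduction and 4.0% with a 75% reduction. The direction is then correct.

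**The case against.** The strongest reply is that the reversal may not occur in this trial.

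First, the documents do not establish that opioid use here is mainly intermittent. Protocol 1.1 describes painful chronic symptoms in most patients, and chronic pain is itself assessed. A regular user counts at baseline whatever the window length. Take an assumed mix of 60% daily users who become intermittent (2 per year) and 40% intermittent users (falling from 4 to 1 per year):
- Baseline: 0.6 + 0.4 × 0.280 = 71%.
- 6-month interval: 0.6 × 0.632 + 0.4 × 0.393 = 54%.

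The group figure falls.

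Second, the trial plans for a large effect. SAP 3.1 assumes 80% achieve VOE-CR over 12 months. Under the same model that is a rate of −ln(0.8) = 0.223 per year, an 89% fall from 2. The 6-month figure is then 1 − exp(−0.223 × 0.5) = 10.6%, below the 15.1% baseline.

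Third, the >6-12 and >12-18 month intervals are equal to each other, so the later trend can be read. Listings and annualized VOE and hospitalization summaries, with PROMIS pain scores, also bear on pain burden. The endpoint is descriptive, and the distortion runs against the product.

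All of this stands, and it limits the point to intermittent users with falls below the break-even. It does not make the baseline column comparable with the later ones. Even when the direction is right, the size of the change is understated: 15.1% to 10.6% for an 89% fall. Listings are not a planned summary, and none of the other measures is opioid use.

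**Conclusion.** The baseline percentage and the percentages after Month 3 are not comparable. This follows from the stated window lengths alone. The size of the distortion rests on an assumed constant rate of intermittent use: falls smaller than about 84% in the 6-month intervals, or 67% in >3-6 months, appear as increases. Under that model the thresholds do not depend on the starting rate; the example percentages do.

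A reader might go further and infer that the endpoint cannot be answered, that the table will show worsening, or that opioid use in Days 1-90 has nothing to do with sickle cell disease. The documents support none of these. Falls beyond the break-even show as improvement, regular users are not affected in this way, and the records allow a valid summary. The first 90 days fall in the transplant and recovery period, which complicates interpretation but does not exclude disease-related use.

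The consequence is limited to an exploratory, descriptive table. Primary and key secondary conclusions are unaffected.

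**What to change.** In SAP 4.4.4, make the comparison with baseline in windows of equal length: the percentage with any opioid use in the 30 days before consent and in the 30 days ending at Months 6, 12, 18 and 24, with oral and non-oral use shown separately. Lengthening the baseline is not the practical route, because prior medication is collected for only 30 days. Keep the existing intervals as a supplementary description, labelled as not for comparison with baseline.

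The cost is SAP wording and one reprogrammed table. Concomitant medications are already collected continuously from consent, so no new data are needed.

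The downside is that snapshots miss use between look-backs and depend on medication dates. SAP Appendix 6.1 sets wholly missing end dates to data cut-off or end of study, so a record with an imputed end date could count as use in every later look-back. Such records should be flagged. Opioid-days per 30 days would cover the gaps but is fragile for the same reason. It also needs actual days of use, and an as-needed opioid may be recorded as ongoing.

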4.4.5. Analysis of Correlation

The following exploratory correlation analyses, but may not be limited to, will be conducted:

- VOE-CR (Yes or No) (in TPVOE for Group C and Overall) versus:
 - Globin Response (Yes or No)
 - VOE-CR24 (Yes or No)
 - sVOE-CR24 (Yes or No)
 - non-transfused HbA^{T87Q} (% of non-transfused total Hb) at Month 6
 - DP VCN (c/dg)
 - DP %LVV+ cells
 - Total CD34+ cells (10⁶/kg) infused
 - PB VCN (c/dg) at Month 6
 - PB %LVV+ cells at Month 6
- sVOE-CR (Yes or No) (in TPVOE for Group C and Overall) versus:
 - Globin Response (Yes or No)
 - sVOE-CR24 (Yes or No)
 - non-transfused HbA^{T87Q} (% of non-transfused total Hb) at Month 6
 - DP VCN (c/dg)
 - DP %LVV+ cells
 - Total CD34+ cells (10⁶/kg) infused
 - PB VCN (c/dg) at Month 6
 - PB %LVV+ cells at Month 6
- Globin response (Yes or No) (in TP for Group C and Overall) versus:
 - VOE-CR24 (Yes or No)
 - sVOE-CR24 (Yes or No)
 - non-transfused HbA^{T87Q} (% of non-transfused total Hb) at Month 6
 - DP VCN (c/dg)
 - DP %LVV+ cells
 - Total CD34+ cells (10⁶/kg) infused
 - PB VCN (c/dg) at Month 6
 - PB %LVV+ cells at Month 6
- HbA^{T87Q} (% of non-transfused total Hb in TP for Group C and Overall) at Month 6 versus:
 - Change (%) from baseline in annualized number of adjudicated sVOEs
 - Change (%) from baseline in annualized number of adjudicated VOEs

- DP VCN (c/dg)
- DP %LVV+ cells
- Total CD34+ cells ($10^6/\text{kg}$) infused
- PB VCN (c/dg) at Month 6
- PB %LVV+ Cells at Month 6
- HbS (% of non-transfused total Hb) at Month 6

Scatter plots for DP VCN (c/dg) and DP %LVV+ Cells versus HbA^{T87Q} (% of non-transfused total Hb) at Month 6 for TP Group C and Overall will be provided to explore whether there is a positive correlation trend between these drug product characteristics and HbA^{T87Q} (%) at Month 6. For this analysis, data may be transformed as appropriate.

- Non-HbS (% of non-transfused total Hb in TP for Group C and Overall) at Month 6 versus:
 - Change (%) from baseline in annualized number of adjudicated sVOEs
 - Change (%) from baseline in annualized number of adjudicated VOEs
- HbA^{T87Q} (% of non-transfused total Hb in TP for Group C and Overall) at Month 6 versus:
 - Change from baseline in total bilirubin at Month 6
 - Change from baseline in indirect bilirubin at Month 6
 - Change from baseline in lactate dehydrogenase at Month 6
 - Change from baseline in reticulocytes at Month 6
- Non-HbS (% of non-transfused total Hb in TP for Group C and Overall) at Month 6 versus
 - Change from baseline in total bilirubin at Month 6
 - Change from baseline in indirect bilirubin at Month 6
 - Change from baseline in lactate dehydrogenase at Month 6
 - Change from baseline in reticulocytes at Month 6

For each correlation analysis, all specified subjects will be included in the analysis, providing they have non-missing data in both endpoints for the correlation. For correlation between 2 binary outcomes, between 2 continuous outcomes, and between 1 continuous and 1 binary outcome, the Kappa score, Pearson correlation coefficient, and Mann-Whitney test, respectively, will be performed.

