7.4.4.5. Correlation Analyses between Efficacy Endpoints

The following correlation analyses will be performed:

- Globin Response vs VOE-CR
- Globin Response vs sVOE-CR
- HbA^{T87Q} percentage at Month 6 vs percent change in annualized sVOEs

Details of the correlation analyses will be provided in the SAP.

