3. GENERAL STATISTICAL METHODS

3.1. Sample Size Justification

The sample sizes for Groups A and B are not determined by formal statistical methods.

Approximately 41 subjects will be enrolled in Group C with approximately 35 subjects meeting the severe VOE criteria as defined in Inclusion Criterion #3.1.

- For the primary endpoint, VOE-CR: assuming 80% of Group C subjects in the TPVOE will meet the primary efficacy endpoint, 35 subjects will provide more than 99% power to reject the null hypothesis of 40% at 1-sided alpha of 0.025, using the Exact Test per EAST® (Version 6). The success criterion is 60% (21 out of 35) of subjects meeting the primary efficacy endpoint, if exactly 35 subjects with at least 4 VOEs in the 24 months prior to ICF are enrolled and receive drug product in Group C.
- For the key secondary endpoint, sVOE-CR: assuming 85% of Group C subjects in the TPVOE will meet the primary efficacy endpoint under the alternative hypothesis, 35 subjects will provide more than 99% power to reject the null hypothesis of 50% at 1-sided alpha of 0.025, using the Exact Test per EAST® (Version 6). The success criterion is 69% (24 out of 35) of subjects meeting the key secondary endpoint, if exactly 35 subjects who have at least 4 VOEs in the 24 months prior to ICF are enrolled and received drug product in Group C.
- For the key secondary endpoint, Globin Response: assuming 70% of Group C subjects in the TP will meet the key secondary efficacy endpoint under the alternative hypothesis, 41 subjects will provide approximately 96% power to reject the null hypothesis of 40% at 1-sided alpha of 0.025, using the Exact Test per EAST® (Version 6). The success criterion is 59% (24 out of 41) of subjects meeting the key secondary efficacy endpoint, if exactly 41 subjects are enrolled and received drug product in Group C.

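### SAP 4.4.5 summarises the link between Globin Response and VOE resolution with kappa, an agreement index that cannot exceed about 0.74 (VOE-CR) or 0.58 (sVOE-CR) at the planned rates and does not show resolution by globin status

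*SAP*

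**What the plan says.** Protocol 7.4.4.5 names three correlation analyses. The first is "Globin Response vs VOE-CR", the second pairs Globin Response with sVOE-CR, and the third pairs Month 6 HbA-T87Q percentage with percent change in annualized sVOEs. The protocol names no statistic and leaves the details to the SAP.

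SAP 4.4.5 opens with "The following exploratory correlation analyses, but may not be limited to, will be conducted". One block begins "VOE-CR (Yes or No) (in TPVOE for Group C and Overall) versus" and lists Globin Response first. A parallel block does the same for sVOE-CR, and a third sets Globin Response against VOE-CR24 and sVOE-CR24. The closing paragraph assigns the methods by variable type: "the Kappa score, Pearson correlation coefficient, and Mann-Whitney test, respectively, will be performed". For two binary outcomes that means kappa. The section specifies no cross-tabulation, conditional rate, confidence interval or test to go with it.

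The planned rates are in SAP 3.1: "assuming 80% of Group C subjects in the TPVOE will meet the primary efficacy endpoint" for VOE-CR, 85% in the sVOE-CR bullet, and "assuming 70% of Group C subjects in the TP will meet the key secondary efficacy endpoint under the alternative hypothesis" for Globin Response.

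**The concern.** Kappa asks whether two classifications of the same attribute agree beyond chance. Globin Response is a laboratory composite and VOE-CR is a clinical event endpoint, and the plan expects them to occur at different rates. Kappa counts a subject who resolves without Globin Response as a disagreement, exactly as it counts a globin responder who still has events. Clinically the two mean different things: only the second speaks against globin response being sufficient for resolution.

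This has two consequences. Because the marginal rates differ, kappa has a ceiling below 1 even when no globin responder fails. And the number does not tell the reader whether globin responders resolve more often, or by how much. That question follows from the protocol's endpoint rationale (1.3.2), which expects correction of anemia to go with correction of other disease manifestations. A lone kappa of, say, 0.5 could be close to the ceiling or a moderate link, and the planned output would not tell these apart.

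**Working it through.** **Planned rates.** The documents state no kappa or association strength, so I first confirmed the power figures attached to the planned rates, using the exact binomial P(X ≥ k).
- VOE-CR: n = 35, k = 21, rate 80%, power 0.998 (plan: above 99%); actual one-sided alpha at 40% is 0.0133.
- sVOE-CR: n = 35, k = 24, rate 85%, power 0.996 (plan: above 99%); actual alpha at 50% is 0.0205.
- Globin Response: n = 41, k = 24, rate 70%, power 0.959 (plan: about 96%); actual alpha at 40% is 0.0126.

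The plan's figures reproduce. The 70% is stated for the TP; I assume it also holds in the TPVOE, where the pairs with VOE-CR and sVOE-CR are analysed.

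**Formulas.** Let a be the resolution rate, b the Globin Response rate and p the proportion with both. Observed agreement is po = 1 − a − b + 2p. Chance agreement is pe = ab + (1 − a)(1 − b). Kappa = (po − pe)/(1 − pe).

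**Ceiling.** If every globin responder resolves, p = b = 0.70.
- VOE-CR (a = 0.80): po = 0.90, pe = 0.56 + 0.06 = 0.62, kappa = 0.28/0.38 = 0.737.
- sVOE-CR (a = 0.85): po = 0.85, pe = 0.595 + 0.045 = 0.64, kappa = 0.21/0.36 = 0.583.

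**A given strength of link.** For an odds ratio R, p solves p(1 − a − b + p) = R(a − p)(b − p). R is my assumption; the documents give none.
- R = 6, 80%/70%: p = 0.625, po = 0.751, kappa = 0.131/0.38 = 0.34. Resolution is 0.625/0.70 = 89% in globin responders and 0.175/0.30 = 58% in non-responders.
- R = 6, 85%/70%: p = 0.648, po = 0.746, kappa = 0.106/0.36 = 0.29. Resolution is 92.5% against 67%.
- R = 6, 50%/50%: kappa 0.42. The same odds ratio gives a smaller kappa at the planned rates.
- R = 10, 20 and 50: kappa 0.43, 0.53 and 0.63 at 80%/70%, and 0.37, 0.45 and 0.52 at 85%/70%.

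**Whole tables at n = 35, every globin responder resolving.**
- 28 VOE-CR, 25 Globin Response (25 both, 3 VOE-CR only, 0 globin only, 7 neither): po = 32/35 = 0.914, pe = (28×25 + 7×10)/35² = 0.629, kappa = 0.77.
- 30 sVOE-CR, 25 Globin Response (25, 5, 0, 5): po = 30/35 = 0.857, pe = (30×25 + 5×10)/35² = 0.653, kappa = 0.59. Resolution is 25/25 against 5/10, Fisher p = 0.0008. The two rates are far easier to read than 0.59.

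**How often kappa comes out small.** In 200,000 simulated trials of 35 at 80%/70%, kappa fell below 0.2 in 10.3% and to 0 or below in 1.2% at odds ratio 10; at odds ratio 20 the figures were 3.2% and 0.3%. The phi coefficient, the ordinary correlation of two binary variables, fell below 0.2 in 8.7% and 2.4%.

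**The case against.** The strongest reply is that kappa does little harm here, and much of it stands.

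- **Kappa does not vanish at the planned rates.** A reader might infer that a strong link could look absent. The figures do not support that: odds ratio 6 gives 0.34 and 0.29, and complete nesting gives 0.59 to 0.77. Phi is close (0.36 and 0.32 at odds ratio 6) and also falls as rates rise. Collapse needs response near 100%; at 97%/85% the ceiling is 0.30. So few non-responders then remain that every measure is weak.
- **A negative kappa at high rates need not hide anything.** With 33/35 and 30/35 responders and 80% agreement, kappa is −0.09. But those margins force the table 28, 5, 2, 0, with resolution in 28/30 globin responders and 5/5 non-responders (Fisher p = 1.0). There is no positive link to miss.
- **Fisher's test is no cure for small numbers.** At odds ratio 6 and n = 35 its simulated power at two-sided 0.05 is about 46% at 80%/70%. The remedy should rest on rates and an interval, with any p-value descriptive.
- **The analyses are exploratory, and the question has other support.** VOE-CR and sVOE-CR are also compared with continuous Month 6 HbA-T87Q by Mann-Whitney. All efficacy endpoints are listed by subject (SAP 4.4), so the table could be rebuilt.
- **Kappa suits some pairs.** VOE-CR against VOE-CR24, and sVOE-CR against sVOE-CR24, are the same endpoint over overlapping windows, and agreement is a fair question there.

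These points limit the impact. They do not make kappa answer whether globin responders resolve more often.

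**Conclusion.** The point holds as a minor improvement. For Globin Response against the VOE resolution endpoints, kappa is the wrong kind of summary: it is capped at about 0.74 and 0.58 at the planned rates, understates a given odds ratio relative to balanced rates, and omits the resolution rate by globin status. It does not bear on the primary or key secondary tests. The ceilings rest on the SAP 3.1 rates and on 70% Globin Response carrying over to the TPVOE; the values below the ceiling also rest on the assumed odds ratios.

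One might extend the criticism to Pearson for percent change in VOEs or sVOEs, which is bounded at −100%, where many subjects may cluster. No calculation here shows that Pearson misleads, and Spearman would face heavy ties at the bound, so this is an option and not a finding.

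**What to change.** Amend the closing paragraph of SAP 4.4.5. For Globin Response against VOE-CR, sVOE-CR, VOE-CR24 and sVOE-CR24, report:
- the 2x2 table;
- the resolution rate in globin responders and in non-responders;
- an exact 95% confidence interval for the difference in rates or the odds ratio, with Fisher's p-value labelled descriptive.

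These may replace kappa or stand beside it. Keep kappa, if wanted, for VOE-CR against VOE-CR24 and sVOE-CR against sVOE-CR24. Optionally, add Spearman beside Pearson where one variable is percent change in annualized VOEs or sVOEs.

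The cost is one sentence in the SAP and one small exploratory table per pair, with no new data. The intervals will be wide at n = 35, which is itself useful to the reader.
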